5.1.13.3 Respiratory system

In case of abnormal spirometry results or persistent respiratory symptoms (e.g., dyspnea), the subject will be closely observed, spirometry will be repeated, and study drug discontinuation should be considered, according to the guidance provided in Table 5.

Item	Parameter	Guidance
1	If: > 30% decrease from the study baseline FEV ₁ and/or FVC.	Repeat PFT within the next 2 weeks or earlier if clinically indicated. See item 1a, 1b.
1a	If at repeat PFT: > 30% decrease from the study baseline FEV1 and/or FVC and, in the opinion of the investigator, this change is clinically significant.	Discontinue study drug and perform FU PFTs.
1b	If at repeat PFT: ≤ 30% decrease from the study baseline FEV ₁ and/or FVC and the subject does not have respiratory symptoms (e.g., cough, dyspnea)	Resume regular PFTs schedule.

Table 5	Guidance for subject monitoring and discontinuation for PFT
	decrease and persistent respiratory AEs

AE = adverse event; FEV₁ = forced expiratory volume in 1 second; FU = follow-up; FVC = forced vital vapacity; PFT = pulmonary function test.

If clinically significant, persistent respiratory AEs (e.g., dyspnea) are reported, PFTs must be performed and study drug may be interrupted at the discretion of the investigator. In case of study drug interruption, the subject will be closely observed, FU PFTs will be performed, and further diagnostic work-up and consultation with a pulmonologist or other specialist should be considered according to local practice and the clinical situation. Following study drug interruption, if PFTs normalize and lung toxicity is unlikely, study drug may be re-initiated at the discretion of the investigator.

The decision to permanently discontinue study drug will be made after evaluation of all available information concerning concomitant medications, other potential causes of respiratory AEs, and the clinical status of the subject. Further diagnostic work-up and

consultation with a pulmonologist or other specialist should be considered according to local practice and the clinical situation.

Subjects experiencing respiratory symptoms and/or reduced pulmonary function during the course of the treatment with the study drug may be prescribed short-acting β_2 agonist (to be used on 'as needed' basis / 'PRN' use), at the investigator's discretion. If a subject fails to show symptom relief and/or reversibility, additional diagnostic work-up (e.g., high-resolution computerized tomography, DL_{CO}) and/or permanent study drug discontinuation should be considered at the discretion of the investigator.

In all cases of permanent discontinuation, FU monitoring must be provided until respiratory AEs have resolved and changes in pulmonary function are no longer regarded as clinically relevant, or until medically indicated.

5.1.13.4 Pregnancy

If a subject becomes pregnant while on study drug, study drug **must** be permanently discontinued. The investigator must counsel the subject and discuss the risks of continuing with the pregnancy and the possible effects on the fetus. If the subject wishes to continue pregnancy, Actelion Global Drug Safety will request the unblinding of the treatment assignment and only the subject allocated to teriflunomide will perform an accelerated elimination procedure [see Section 5.1.14].

If a female partner to a male study participant becomes pregnant while the study participant is on study drug, the study drug in the male subject **must** be permanently discontinued. Actelion Global Drug Safety will request the unblinding of the treatment assignment. In case the male subject has been on teriflunomide, the investigator must counsel the subject and discuss the risks of continuing with the pregnancy and the possible effects on the fetus. If the subject was on ponesimod, there is no risk for the female partner to continue pregnancy. The accelerated elimination procedure will be performed in the male subject only if the subject was on teriflunomide.

Male and female subjects participating in the study and wishing to father a child or wishing to become pregnant during the study must discontinue study drug, perform an accelerated elimination procedure, and continue contraception as indicated per protocol until 6 weeks after the first of two tests indicating serum teriflunomide level < 0.02 mg/L.

5.1.13.5 Liver abnormalities

In case of abnormal liver tests or signs and symptoms suggestive of drug induced liver injury (DILI), the subject will be closely observed, liver tests will be repeated, and study drug discontinuation should be considered according to the guidance provided in Table 6.
EudraCT 2012-000540-10 Doc No D-18.388

Confidential

5 December 2018, page 109/376

Guidance for subject monitoring and discontinuation for liver Table 6 enzyme abnormalities

Item	Laboratory parameter	Guidance
1	ALT or AST \geq 3 × ULN *	Start close observation. Repeat labs within 72 hours. See items 1a and 1b. * if ALT or AST \ge 8 × ULN OR ALT or AST \ge 3 × ULN and TBL \ge 2 × ULN or INR > 1.5 OR ALT or AST \ge 3 × ULN with the appearance of fatigue, nausea, vomiting, right upper quadrant pain or tenderness, fever, rash, and/or eosinophilia (> 5%) and retest cannot be done within 72 h, permanently discontinue study drug, and perform FU.
1a	If at repeated labs, ALT or AST $\geq 3 \times ULN < 8 \times ULN$	Continue close observation. Repeat labs twice weekly. See items 2a and 2b.
1b	If at repeated labs, ALT or AST < 3 × ULN	Resume regular labs schedule.
2a	If at repeated labs, ALT or AST $\geq 5 \times ULN$ for > 2 weeks	Permanently discontinue study drug, and perform FU.
2b	If at repeated labs, ALT or AST \geq 3 × ULN < 5 × ULN for > 2 weeks	Continue close observation. Repeat labs once or twice weekly.
3	 If at repeated labs: ALT or AST ≥ 8 × ULN ALT or AST ≥ 3 × ULN and TBL ≥ 2 × ULN or INR > 1.5 × ULN ALT or AST ≥ 3 × ULN with the appearance of fatigue, nausea, vomiting, right upper quadrant pain or tenderness, fever, rash, and/or eosinophilia (> 5%) 	Permanently discontinue study drug, and perform FU.

ALT = alanine aminotransferase; AST = aspartate aminotransferase; FU = follow-up; INR = International Normalized Ratio; ULN = upper limit of normal range.

Whenever AST or ALT \ge 3 × ULN are recorded by the central laboratory, an alert will be sent to the principal investigator and the sponsor. The sponsor will contact the principal investigator to ensure that she/he will immediately contact the subject, and ask the subject about any potential symptoms. The subject will be closely observed and will be asked to

Ponesimod / ACT-128800 **Relapsing multiple sclerosis** Protocol AC-058B301, OPTIMUM Version 7

Confidential

5 December 2018, page 110/376

return to the site as soon as possible after the time of receipt of the alert to repeat the liver enzyme and bilirubin tests by the central laboratory (unless the clinical situation mandates immediate local testing) according to the scheme illustrated in Table 6. Further diagnostic work-up and consultation with a hepatologist or other specialist should be considered, and adequate medical management should be provided according to local practice and the clinical situation. Any clinically relevant finding meeting the definition of an AE will be recorded accordingly in the eCRF.

In case of study drug interruption, the subject will be closely observed and FU liver tests will be performed. Following study drug interruption, if liver tests normalize and drug-related hepatotoxicity is unlikely, study drug may be re-initiated at the discretion of the investigator. Re-initiation following interruption according to the above criteria can only be done once during the study. The decision to permanently discontinue study drug will be made after evaluation of all available information concerning concomitant medications, other potential causes of hepatotoxicity, and the clinical status of the subject. NB: The re-initiation is not permitted for situations where the study drug should be permanently discontinued according to Table 6. In all cases of permanent study drug discontinuation, FU monitoring must be provided until signs and symptoms have resolved and changes in liver function are no longer regarded as clinically relevant or until medically indicated.

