- (17) Pulmonary function tests include spirometry to be performed pre-dose in all subjects and DL_{CO} to be performed in a subset of approximately 400 subjects at selected sites only.
- (18) In addition, liver tests (ALT, AST, INR, alkaline phosphatase and total bilirubin) at Weeks 6, 8, 10, 14, 16, 18, 20, and, 22 will be collected, sent to, and analyzed at the central laboratory. Furthermore, total white blood cell and total lymphocyte counts will be assessed at Weeks 8, 16, and 20. The test window is ± 3 days. Note: No relapse assessment questionnaire is needed when blood sample is drawn.
- (19) Serum pregnancy test at Screening, urine pregnancy test at all subsequent visits. Urine pregnancy tests (performed at home) on a 4-weekly (+/- 4 days) basis between the visits during the study (results to be communicated by telephone call to the principal investigator / treating neurologist). At all visits and telephone calls, the methods of contraception will be reviewed and the contraceptive method form entered in the eCRF must be updated as applicable.

(20) Pharmacokinetic sampling pre-dose at Weeks 12, 60 and 108, and 3 h (+/-15 min) post-dose on Day 1 and Week 12.

(21) Scheduled study medication dispensing/return procedures may be adapted according to the site practice.

(22) All AEs and SAEs that occur after signing the Informed Consent Form and up to 30 days after study treatment discontinuation must be reported.

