5.1.12 Premature discontinuation of study treatment

In the study, the premature discontinuation of study treatment is defined as a permanent discontinuation of study treatment earlier than the planned treatment duration of 108 weeks. The decision to prematurely discontinue study treatment may be made by the subject, the investigator or Actelion.

A subject has the right to prematurely discontinue study treatment at any time by withdrawal from treatment only or by withdrawal from treatment and any further participation in the study.

The investigator should discontinue study treatment for a given subject if, on balance, she/he believes that continued administration would be contrary to the best interests of the subject. In case of clinically significant progression of the disease as judged by the investigator, the investigator should consider switching to another potentially more effective therapy, discuss alternative treatment options with the subject, and document the outcome of this discussion in the medical records.

Premature discontinuation of study treatment may also result from a decision by Actelion, e.g., in case of premature termination or suspension of the study [see Section 9.3].

The main reason and whether discontinuation of study treatment is the decision of the subject, the investigator, or Actelion must be documented in the eCRF.

A subject who prematurely discontinues study treatment is NOT considered as withdrawn from the study and will be followed up until Week 108 in the PTOP or until the end of the safety FU period (30 days after study drug discontinuation), whichever comes last [see

Section 3.1.3], provided that the subject's consent for this limited participation in the study has not been withdrawn.

A subject who prematurely discontinues study treatment and withdraws consent to participate in any further study assessments is considered withdrawn from the study. Subjects who die or are lost to FU are also considered as withdrawn from the study. Withdrawal from the study and FU medical care of subjects withdrawn from the study is described in Sections 9.2 and 9.4, respectively.

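### Table 6 gives the same liver stopping criterion two INR limits (> 1.5 in item 1, > 1.5 × ULN in item 3), so a confirmed result can lead to a weaker action than the same result unconfirmed

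*Protocol*

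**What the plan says.** Section 5.1.13.5, Table 6, starts from an ALT or AST of at least 3 × ULN and asks for repeat labs within 72 hours.

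- **Item 1, asterisked note.** It lists three alternatives: ALT or AST ≥ 8 × ULN; ALT or AST ≥ 3 × ULN together with bilirubin ≥ 2 × ULN or a raised INR; ALT or AST ≥ 3 × ULN with listed symptoms or eosinophilia > 5%. The INR part reads "ULN or INR > 1.5 OR ALT or AST". The note applies when the "retest cannot be done within 72 h, permanently discontinue study drug, and perform FU".
- **Item 3.** It lists the same three alternatives for repeated labs, with the same action. The INR part reads "ULN or INR > 1.5 × ULN".
- **Item 1a.** For a repeat ALT or AST of 3 to < 8 × ULN: "Continue close observation. Repeat labs twice weekly. See items 2a and 2b".
- **Item 2a.** ALT or AST ≥ 5 × ULN for more than 2 weeks leads to permanent discontinuation.
- **Item 2b.** For ALT or AST of 3 to < 5 × ULN for more than 2 weeks: "Continue close observation. Repeat labs once or twice weekly".

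INR is collected. Table 1, note 18, adds "liver tests (ALT, AST, INR, alkaline phosphatase and total bilirubin" at the central laboratory at eight further draws between Weeks 6 and 22.

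The text after Table 6 rules out restarting study drug wherever the table calls for a permanent stop.

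**The concern.** The two rows differ in one element only. If the sponsor wanted a more cautious rule for a result that cannot be rechecked in time, the transaminase and bilirubin limits would be expected to be lower in item 1 as well. They are the same, which points to a drafting slip.

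With an INR ULN above 1.0, item 3 is the laxer row. A repeat that confirms raised transaminases with impaired coagulation then calls for less than the same finding left unconfirmed.

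Liver injury is a recognised risk here. Section 1.3.3 reports severe and fatal liver injury with leflunomide and expects a similar risk with teriflunomide. Section 1.3.2.4 reports transaminase elevations with ponesimod. Because a Table 6 stop is final, the choice of INR limit also decides whether a subject may go back on drug.

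**Working it through.** **Inputs**

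- Item 1 INR limit: 1.5, absolute (Table 6, item 1 note).
- Item 3 INR limit: 1.5 × ULN (Table 6, item 3).
- INR ULN: not given in the protocol pages reviewed. Assumed range 1.0 to 1.3.

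**Side-by-side comparison**

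| Element | Item 1 note (no retest within 72 h) | Item 3 (repeated labs) |
|---|---|---|
| ALT/AST alone | ≥ 8 × ULN | ≥ 8 × ULN |
| ALT/AST in combination | ≥ 3 × ULN | ≥ 3 × ULN |
| Bilirubin | ≥ 2 × ULN | ≥ 2 × ULN |
| Symptoms; eosinophilia | same list; > 5% | same list; > 5% |
| INR | > 1.5 | > 1.5 × ULN |
| Action | permanent stop | permanent stop |

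**Width of the discordant band**

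Width = 1.5 × ULN − 1.5.

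| Assumed INR ULN | Item 3 limit | Width |
|---|---|---|
| 1.0 | 1.50 | 0 |
| 1.1 | 1.65 | 0.15 |
| 1.2 | 1.80 | 0.30 |
| 1.3 | 1.95 | 0.45 |

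Below a ULN of 1.0 the order reverses: at 0.9 the item 3 limit is 1.5 × 0.9 = 1.35, and item 3 becomes the stricter row.

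**Worked subject:** ALT 4 × ULN, bilirubin 1 × ULN, no listed symptom, eosinophils ≤ 5%, INR 1.6.

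1. No retest within 72 h: 1.6 > 1.5, so item 1 calls for a permanent stop.
2. Retest gives the same values: 1.6/1.1 = 1.45, 1.6/1.2 = 1.33 and 1.6/1.3 = 1.23. All are below 1.5 × ULN, so item 3 is not met. This holds for any ULN of at least 1.6/1.5 = 1.07.
3. Item 1a then applies: observation with labs twice a week.
4. If the values stay where they are for more than 2 weeks, item 2b applies: further observation. No row of the table calls for a stop.

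If the same subject had ALT of 5 to < 8 × ULN, item 2a would stop the drug, but only after more than 2 weeks. At two panels a week that is about four repeat panels.

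The INR limit alone decides the action only when ALT/AST is 3 to < 8 × ULN, bilirubin is < 2 × ULN, there is no listed symptom and eosinophils are ≤ 5%. The discrepancy remains whether INR is read as an alternative to bilirubin within the ALT/AST condition or as a criterion on its own.

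**The case against.** The strongest reply is that the two rows govern different situations and no single result is judged by both. Stopping at a lower INR when no confirmation can be had, and watching closely when it can, is a coherent precaution. That cannot be excluded, but the protocol does not say it, and the matching limits elsewhere in the two rows make it unlikely.

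Second, Section 5.1.13.5 presents the table as guidance and leaves room for judgement: "The decision to permanently discontinue study drug will be made after evaluation of all available information". Section 5.1.12 adds "The investigator should discontinue study treatment for a given subject if, on balance" continued treatment is against the subject's interests. The sponsor contacts the investigator after every ALT or AST alert, Section 5.1.9 allows interruption for a laboratory abnormality, and specialist consultation is to be considered. A subject in the band is therefore under observation, not overlooked. This limits the harm. It does not tell a site which limit the protocol intends, and the bar on restarting gives the table's stops binding force.

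Third, the evidence that INR is measured comes from the scheduled draws. The text after Table 6 describes the repeat as liver enzymes and bilirubin and does not name INR. Section 7.3.14.2 and Appendix 6 were not among the pages reviewed and may settle this. The point stands as a caveat, though item 3 presupposes that an INR is available at the repeat.

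Fourth, the clinical consequence depends on an INR ULN that has not been seen. That is correct, and the conclusion is conditional on it.

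**Conclusion.** The contradiction is certain from the wording of Table 6: one criterion, two INR limits, no stated reason. The clinical consequence is conditional. If the INR ULN exceeds 1.0, there is a band, 0.15 to 0.45 INR units wide for an assumed ULN of 1.1 to 1.3, in which a confirmed result leads to observation and the same unconfirmed result to a permanent stop. At a ULN of exactly 1.0 the rows agree.

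The group is narrow and the documents give no frequency from which to count it. Sample size, power and the primary analysis are not affected. The sponsor should correct it because it is a decision threshold in a liver safety rule.

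**What to change.** Put the same INR limit in both rows. The default should be INR > 1.5 in item 3, the more protective choice if the ULN is above 1.0 and one that does not vary with the testing laboratory's reference range; the text after Table 6 allows local testing when the clinical situation demands it. Using 1.5 × ULN in both rows would also remove the contradiction. If the higher limit at retest is intended, state the clinical reason.

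If the worry is an INR raised by warfarin, which Section 5.2.4 permits with monitoring, write that exception once for both rows, since such an INR can cross either limit. If INR is not already part of the repeat panel, name it there. The laboratory alert needs no change, because it is triggered by ALT or AST ≥ 3 × ULN.

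The cost is one table cell and possibly a few more permanent discontinuations, a number that cannot be estimated from the documents.

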5.1.13.6 Renal function

Subjects **must** be permanently discontinued from study drug at any time throughout the study in the event of a rapid serum creatinine increase to $> 150 \mu mol/L$ or rapid decrease in calculated creatinine clearance to < 30 mL/min (Cockroft-Gault) that cannot be rapidly reversed (by volume repletion or relief of urinary tract obstruction [according to etiology]). Any clinically relevant finding meeting the definition of an AE will be recorded accordingly in the eCRF.

5.1.13.7 Ocular abnormalities

In the event of suspected clinically significant findings (e.g., macular edema), an unscheduled OCT examination should be performed. In the case of macular edema, confirmed by the local ophthalmologist, the subject must be permanently discontinued from study drug and will be managed and followed up until resolution. The OSB will receive all information related to suspected cases of macular edema and will perform central review of OCT results and subject data. Any clinically relevant finding meeting the definition of an AE will be recorded accordingly in the eCRF.

Subjects with active uveitis but without macular edema may continue on the study drug but will require additional ophthalmologic assessments as detailed below:

Ponesimod / ACT-128800 Relapsing multiple sclerosis Protocol AC-058B301, OPTIMUM Version 7 5 December 2018, page 111/376

Confidential

5.1.13.7.1 Guidance for monitoring and management of subjects with uveitis

In case of suspicion of active uveitis (ocular pain, floaters, blurred vision, increased intraocular pressure) at Screening or during a scheduled ophthalmological assessment, fluorescence angiography (FA) should be performed (unless contra-indicated according to the ophthalmologist) in addition to the scheduled ophthalmological assessment and OCT, in order to characterize the uveitis. Subjects with suspicion of uveitis occurring during the study treatment but outside scheduled ophthalmological assessment should have a full ophthalmological assessment performed together with FA (unless contraindicated) as soon as possible. If active uveitis can be confirmed and macular edema can be ruled out, the subject may continue in the study without interrupting the study drug. Such subjects will need to be controlled by the ophthalmologist after 1 week, 2 weeks, and 4 weeks after the diagnosis of uveitis has been confirmed and then every 4 weeks throughout the study or until the condition has resolved. These ophthalmological exams should include full ophthalmological assessment (ophthalmological symptoms, assessment of best corrected visual acuity (Early Treatment Diabetic Retinopathy Study [ETDRS] charts), measurement of ocular pressure, preferably with Goldmann applanation tonometry, slitlamp examination of the anterior segment, and dilated indirect funduscopy) as well as OCT. FA may be repeated at the ophthalmologist's discretion. The ophthalmologist will decide what treatment should be given to the subject. If the subject needs to be treated by immunosuppressants prohibited by the protocol, the study treatment has to be discontinued. If uveitis is progressing in spite of treatment, the investigator may consider interrupting or permanently discontinuing the study drug.

5.1.13.8 Skin reactions

Subjects **must** be permanently discontinued from study drug at any time throughout the study in the event of Stevens-Johnson syndrome or toxic epidermal necrolysis or drug reaction with eosinophilia and systemic symptoms. Subjects will be managed and followed-up until resolution.

5.1.13.9 Peripheral neuropathy

In case of development of symptoms suggestive of peripheral neuropathy such as bilateral numbness or tingling of hands or feet, the investigator should evaluate the subject and decide whether the diagnosis of peripheral neuropathy is likely. Such evaluation may include further clinical and/or neurophysiological diagnostic work-up for peripheral neuropathy according to the local practice. If, as a result of such evaluation, diagnosis of peripheral neuropathy is likely according to the investigator, the subject must be permanently discontinued from study drug, managed and followed up until resolution. Any clinically relevant finding meeting the definition of an AE will be recorded accordingly in the eCRF.

5.1.14 Elimination of teriflunomide

5.1.14.1 Accelerated elimination procedure for teriflunomide

Teriflunomide is eliminated slowly from plasma. Without an accelerated elimination procedure, it takes on average 8 months to reach plasma concentrations less than 0.02 mg/L, although because of individual variations in drug clearance it may take as long as 2 years.

At EOT, all subjects will have to undergo an accelerated elimination procedure consisting of either of the following procedures:

- Administration of cholestyramine 8 g three times a day (i.e., every 8 h) for 11 days. If cholestyramine 8 g three times a day is not well tolerated, cholestyramine 4 g three times a day can be used.
- Administration of 50 g oral activated charcoal two times a day (i.e., every 12 h) for 11 days.

If either elimination procedure is poorly tolerated, treatment days do not need to be consecutive unless there is a need to lower teriflunomide plasma concentration rapidly. It is permissible to switch from cholestyramine to activated charcoal (or vice versa) for reasons of tolerability.

